8.3. Vital Signs

Vital signs will be measured at Screening, Day -3 (Cohorts 4 through 10 only), Day -1 (Cohorts 1 through 3 only), Day 1 (30 minutes prior to the initiation of the study drug infusion, and at 0.5, 0.75, 1, 2, 4, 8 hours after initiation of the study drug infusion), Day 2 (at 24, 30, and 36 hours after initiation of the study drug infusion), Day 3 (at 42 and 48 hours after the initiation of the study drug infusion), Day 4, Day 7, Day 28/EOS. Vital sign

measurements will include systolic and diastolic blood pressures, oral body temperature, respiratory rate, and heart rate.

During the initial 30 minutes of study drug infusion, systolic and diastolic blood pressures and heart rate will be collected every 5 minutes.

Vital signs results will be presented in a data listing sorted by treatment group, subject, and collection date/time. Actual results and change from baseline will be summarized for the safety population.

8.4. Twelve-Lead Electrocardiogram and Telemetry Monitoring

Triplicate 12-lead ECGs will be obtained after the subject has been in the supine position for at least 10 minutes at Screening, within 1 hour prior to the initiation of the study drug infusion, and at 1 hour, 4 hours, 5 hours, 24 hours, and 48 hours after the initiation of the study drug infusion, and on Day 7 and Day 28/EOS and as indicated by AEs or telemetry findings. Electrocardiogram assessments will include comments on whether the tracings are normal or abnormal, rhythm, presence of arrhythmia or conduction defects, morphology, any evidence of myocardial infarction, or ST-segment, T-Wave, and U-Wave abnormalities. In addition, measurements of the following intervals will be measured and reported: RR interval, PR interval, QRS width, and Fridericia-corrected QT interval (QTcF). The investigator will determine whether any of the 12-lead ECG results are clinically significant or not.

If both QT and RR intervals are not missing, the Bazett's-corrected QT interval (QTcB) measured in msec will be calculated using below formula, where RR interval is measured in msec:

$$\bullet \quad QTcB = \frac{QT}{\sqrt{RR/1000}}$$

If both QT and RR intervals are not missing but QTcF interval is missing in the database, QTcF measured in msec will be calculated using below formula, where RR interval is measured in msec:

$$\bullet \quad QTCF = \frac{QT}{\sqrt[3]{RR/1000}}$$

Electrocardiogram results will be presented in data listing sorted by treatment group, subject, and date/time of assessment. In addition, subjects with outlying QTcF, and QTcB intervals (absolute value > 500 msec, absolute value > 480 msec, absolute value > 450 msec, or increase from baseline value >30 or >60 msec) will be listed in a separate data listing based on the International Council for Harmonisation (ICH) harmonized tripartite guideline E14. A summary table will be presented for maximum QTcF and QTcB intervals (including scheduled and unscheduled assessments) meet the outlying criteria using count and percentage.

Actual results and change from baseline will be summarized for the safety population using the average values of the triplicate ECG assessments at each timepoint. Baseline is defined as the last non-missing average value prior to the first study drug administration.

Cardiac telemetry will be collected starting on Day -1 approximately 12 hours prior to the initiation of the study drug infusion (Hour 0) and will continue until subject is discharged from the clinical site for Cohorts 1-9. Cohort 10 subjects will discontinue cardiac telemetry monitoring on Day 3. For Cohorts 4-10, cardiac telemetry monitoring will begin on Day -3 (check in) approximately 12 hours prior to the first dose of Ticagrelor and will be removed once dosed with Ticagrelor. Telemetry assessment results will be listed.

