28. During the MEDI2452 (PB2452) infusion, systolic and diastolic blood pressures and heart rate will be collected every 5 minutes.
- ^g Electrocardiograms will be obtained in triplicate for all subjects at screening, before dosing (within 1 hour prior to the initiation of the MEDI2452 [PB2452] infusion) and at 1, 4 (\pm 30 minutes), 5 (\pm 10 minutes), 24, and 48 hours (\pm 30 minutes) after the initiation of the MEDI2452 (PB2452) infusion and on Days 7 and 28.
- ^h Cardiac telemetry monitoring will begin on Day -1 approximately 12 hours prior to the initiation of the MEDI2452 (PB2452) infusion (Hour 0) and will continue until subject is discharged from the clinical site.
- ⁱ For Cohorts 4 through 9 only: Beginning in the morning on Day -2, ticagrelor will be administered as a single oral dose of 180 mg, followed by 90 mg every 12 hours for 4 additional doses through Hour 0 (ie, 5 total doses of ticagrelor with the 5th dose occurring simultaneously with the initiation of the MEDI2452 [PB2452] infusion).
- ^j For Cohorts 8 and 9 only: On Day 2, ticagrelor will be administered as an additional single dose of 180 mg, 24 hours after the initiation of the MEDI2452 (PB2452) infusion on Day 1 (6th ticagrelor dose).
- ^k For all cohorts: MEDI2452 (PB2452) or placebo will be administered at Hour 0 of Day 1.
- ^l For all cohorts: Blood samples for determination of serum MEDI2452 (PB2452) will be collected within 10 minutes prior to the initiation of MEDI2452 (PB2452) infusion (Hour 0), and at 0.5, 1, 1.5, 2, 3, 4, 6, 8, 12, 24, 48, and 72 hours; and 7 and 28 days after the initiation of the MEDI2452 (PB2452) infusion.
- ^m For Cohorts 4 through 9 only: Blood samples for determination of plasma ticagrelor and AR-C124910XX will be collected within 10 minutes prior to the initiation of MEDI2452 (PB2452) infusion and 5th ticagrelor dose (Hour 0) and at 0.5, 1, 2, 3, 6, 12, and 24 hours after initiation of MEDI2452 (PB2452) infusion and 5th ticagrelor dose.
- ⁿ For Cohorts 8 and 9 only: Additional blood samples for determination of plasma ticagrelor and AR-C124910XX will be collected at 0.5, 1, 2, 3, 6, 12, 24, and 48 hours after Day 2 administration of ticagrelor (6th ticagrelor dose).

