7.3. Study Treatments

The dosing regimens of study drugs in each cohort are as follows:

- Cohort 1: single 30-minute IV infusion of 100 mg MEDI2452 (PB2452) or matching placebo in the morning on Day 1
- Cohort 2: single 30-minute IV infusion of 300 mg MEDI2452 (PB2452) or matching placebo in the morning on Day 1
- Cohort 3: single 30-minute IV infusion of 1000 mg MEDI2452 (PB2452) or matching placebo in the morning on Day 1
- Cohort 4: simultaneous with the 5th ticagrelor dose, a single 30-minute IV infusion of 1000 mg MEDI2452 (PB2452) or matching placebo on Day 1
- Cohort 5: simultaneous with the 5th ticagrelor dose, a single 30-minute IV infusion of 3000 mg MEDI2452 (PB2452) or matching placebo on Day 1
- Cohort 6: simultaneous with the 5th ticagrelor dose, a single 30-minute IV infusion of 9000 mg MEDI2452 (PB2452) or matching placebo on Day 1

- Cohort 7: 2 hours following the 5th ticagrelor dose, a single IV infusion of 18000 mg MEDI2452 (PB2452) or matching placebo on Day 1. The single IV infusion of 18000 mg MEDI2452 (PB2452) or matching placebo will be delivered as a 3000 mg loading dose (41.7 mL) in the first 5 minutes at a rate of 500 mL/hour, followed by a 15000 mg maintenance dose (208.3 mL) delivered over the remaining 7 hours and 55 minutes at a rate of 26.3 mL/hour. The final volume is 250 mL ([Memo Re: PB2452-PT-CL-0001 Cohort 7 Dosing Regimen](#)).
- Cohort 8: 2 hours following the 5th ticagrelor dose, a single IV infusion of 18000 mg MEDI2452 (PB2452) or matching placebo on Day 1. The single IV infusion of 18000 mg MEDI2452 (PB2452) or matching placebo will be delivered as a 6000 mg loading dose (83.3 mL) in the first 15 minutes at a rate of 333 mL/hour, followed by a 6000 mg dose (83.3 mL) over the next 3 hours at a rate of 27.7 mL/hour, and followed by a 6000 mg dose (83.4 mL) over the remaining 8 hours and 45 minutes at a rate of 9.53 mL/hour. The final volume is 250 mL ([Memo Re: PB2452-PT-CL-0001 Cohort 8 Dosing Regimen](#)).

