- Cohorts 9 and 10: 2 hours following the 5th ticagrelor dose, a single IV infusion of 18000 mg MEDI2452 (PB2452) or matching placebo on Day 1. The single IV infusion of 18000 mg MEDI2452 (PB2452) or matching placebo will be delivered as a 6000 mg loading dose (83.3 mL) in the first 15 minutes at a rate of 333 mL/hour, followed by a 6000 mg dose (83.3 mL) over the next 4 hours at a rate of 20.8 mL/hour, and followed by a 6000 mg dose (83.4 mL) over the remaining 12 hours and 5 minutes at a rate of 6.9 mL/hour. The final volume is 250 mL ([Memo Re: PB2452-PT-CL-0001 Cohorts 9 and 10 Dosing Regimens](#)).

Study drug administration data will be presented in a listing.

8. Safety Analysis

Safety and tolerability will be assessed by monitoring and recording of AEs, clinical laboratory test results (hematology, coagulation, serum chemistry, and urinalysis), vital

sign measurements (systolic and diastolic blood pressures, oral body temperature, respiratory rate, and heart rate), ECG results, cardiac telemetry, and physical examination findings.

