10.1. Plasma Pharmacokinetics

10.1.1. Plasma Pharmacokinetics Concentration

Blood samples for PK analysis of total and unbound PB2452 concentration in plasma will be collected from all subjects at the following time points: before dosing (0 hour) and up to 28 days after initiation of the study drug (PB2452 or placebo) infusion. Since ticagrelor is not administered to cohort 1-3 subjects, only unbound PB2452 concentration data will be collected for cohort 1-3 subjects. Specific collection times for each cohort relative to the initiation of the study drug (PB2452 or placebo) infusion on Day 1 are listed in the table below:

Summary of Pharmacokinetic Assessments for PB2452	
Cohorts 1-6	-10 minutes, 0.5, 1, 1.5, 2, 3, 4, 6, 8, 12, 24, 48, and 72 hours, and 7 and 28 days
Cohorts 7-8	-10 minutes 5 minutes and 0.25, 0.5, 1, 2, 3, 4, 6, 8, 8.25, 8.5, 9, 10, 11, 12, 16, 20, 24, 32, and 48 hours, and 7 and 28 days
Cohorts 9-10	-10 minutes, 5 minutes, 0.25, 0.5, 1, 2, 3, 4, 6, 8, 10, 12, 14, 16, 20, 24, 28, 32, 36, 48 hours, 7 and 28 days

Plasma samples for determining total and unbound concentrations of ticagrelor and its active metabolite AR-C124910XX, will be collected from subjects in Cohorts 4 through 10 at the following timepoints: before dosing (within 10 minutes prior to the initiation of the study drug infusion [Hour 0]), and up to 48 hours following the initiation of study drug infusion on Day 1. Of note, subjects in Cohorts 4-6 will be administered the 5th ticagrelor dose and study drug infusion simultaneously, whereas subjects in Cohorts 7-10 will be administered the 5th ticagrelor dose two hours before the study drug infusion initiation on Day 1.

Specific collection times for each cohort relative to the initiation of the study drug (PB2452 or placebo) infusion are listed in the table below:

Summary of Pharmacokinetic Assessments for Ticagrelor and Active Metabolite AR-C124910XX	
Cohorts 4-6	-10 minutes and 0.5, 1, 2, 3, 6, 12, 24 and 48 hours
Cohorts 7-8	-10 minutes, 5 minutes and 0.25, 0.5, 1, 2, 3, 6, 8, 10, 12, 14, 16, 20, 24, 32 and 48 hours
Cohorts 9-10	-10 minutes, 5 minutes, 0.25, 0.5, 1, 2, 3, 6, 8, 12, 14, 16, 20, 24, 28, 36 and 48 hours

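### Cohorts 7–10 are infused for 8 to 16.3 hours on a safety schedule suited to a 30-minute infusion: Cohorts 8–10 have no scheduled vital signs late in the infusion, and Cohort 7 has no scheduled ECG near peak concentration.

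*SAP*

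**What the plan says.** **Infusions.** SAP 7.3 gives stepped 18000 mg regimens. After a 5-minute loading step, the Cohort 7 maintenance dose is "delivered over the remaining 7 hours and 55 minutes at a rate of 26.3 mL/hour". The third step runs "over the remaining 8 hours and 45 minutes at a rate of 9.53 mL/hour" in Cohort 8 and "over the remaining 12 hours and 5 minutes at a rate of 6.9 mL/hour" in Cohorts 9 and 10. In the February 2018 protocol (3.4.2) every infusion lasted 30 minutes.

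**ECGs.** SAP 8.4 schedules triplicate tracings before dosing and at "1 hour, 4 hours, 5 hours, 24 hours, and 48 hours after the initiation of the study drug infusion", then on Days 7 and 28. Table 3-2 footnote g applies these times to all subjects. They are the nominal times of the February protocol.

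**Vital signs.** SAP 8.3 schedules Day 1 readings 30 minutes before the infusion and "at 0.5, 0.75, 1, 2, 4, 8 hours after initiation of the study drug infusion". The next set is at 24 h. It adds: "During the initial 30 minutes of study drug infusion, systolic and diastolic blood pressures and heart rate will be collected every 5 minutes". The February protocol (Table 6-1, footnote f) had: "During the MEDI2452 (PB2452) infusion, systolic and diastolic blood pressures and heart rate will be collected every 5 minutes".

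**Blood draws.** SAP 10.1.1 re-timed PB2452 sampling for the long infusions. The later draws in Cohorts 7–8 are at "8, 8.25, 8.5, 9, 10, 11, 12, 16, 20, 24, 32, and 48 hours, and 7 and 28 days", and Cohorts 9–10 have draws at 10, 12, 14, 16 and 20 h. SAP 11.1 re-timed the pharmacodynamic samples too.

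**The concern.** The sampling for drug and effect follows the new infusions, but the safety readings do not. Safety and tolerability at ascending doses is a primary objective, this is a first-in-human study, and 18000 mg is its top dose. Tables 14.3.5.1 (vital signs) and 14.3.6.1 (ECG) summarise by scheduled time. With nothing scheduled late in the infusion, those tables cannot show a drift in blood pressure, temperature or QTc during that period. SAP 4.6 keeps unscheduled results out of summary tables except for baseline, so readings taken for cause do not fill the rows.

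**Working it through.** **1. Infusion lengths, reproduced from the SAP.** Sum of the stated steps, with volume/rate as a check:

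- Cohort 7: 0:05 + 7:55 = 8:00; 41.7/500 + 208.3/26.3 = 8.00 h
- Cohort 8: 0:15 + 3:00 + 8:45 = 12:00; 83.3/333 + 83.3/27.7 + 83.4/9.53 = 12.01 h
- Cohorts 9–10: 0:15 + 4:00 + 12:05 = 16:20; 83.3/333 + 83.3/20.8 + 83.4/6.9 = 16.34 h

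**2. Infusion left after the last scheduled Day 1 reading.** Final-step rates: 15000/7.917 = 1895 mg/h (Cohort 7), 6000/8.75 = 686 mg/h (Cohort 8), 6000/12.083 = 497 mg/h (Cohorts 9–10). Dose left is time left × final rate, using unrounded rates; percentages are of 18000 mg.

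| | Cohort 7 | Cohort 8 | Cohorts 9–10 |
|---|---|---|---|
| After the last vital signs (8 h) | none | 4.0 h, 2743 mg, 15% | 8.33 h, 4138 mg, 23% |
| After the last ECG (5 h) | 3.0 h, 5684 mg, 32% | 7.0 h, 4800 mg, 27% | 11.33 h, 5628 mg, 31% |

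The vital-signs gap spares Cohort 7, because 8 h is the end of its infusion.

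**3. Dose covered by the 5-minute readings (first 30 minutes).**

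- Cohort 7: 3000 + (25/60) × 1895 = 3789 mg, 21%
- Cohort 8: 6000 + 0.25 × 2000 = 6500 mg, 36%
- Cohorts 9–10: 6000 + 0.25 × 1500 = 6375 mg, 35%

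The whole loading step is covered in each case.

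**4. How near peak are the ECGs?** The documents give no human half-life, so I assume 6–30 h and one compartment. For a step at rate R from a to b, the amount in the body at time t after the step is (R/k)·[e^(−k(t−b)) − e^(−k(t−a))], with k = ln 2/half-life; during the step, the first exponential is 1. Volume cancels in every ratio.

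Cohort 7 keeps rising to the end of infusion if k < 1895/3000 = 0.632 per hour, that is, for a half-life above about 1.1 h. At a 6 h half-life (k = 0.1155) about 2986 mg is in the body after the loading step, and then:

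- 5 h: 2986·e^(−0.1155×4.917) + (1895/0.1155)·(1 − e^(−0.1155×4.917)) ≈ 8799 mg
- 8 h: the same with 7.917 h ≈ 11026 mg
- ratio 8799/11026 = 0.80

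| Best Day 1 ECG as a share of the cohort's own peak | Cohort 7 | Cohort 8 | Cohorts 9–10 |
|---|---|---|---|
| Current (1, 4, 5 h), half-life 6–30 h | 71–80% | 82–100% | 83–100% |
| Current, half-life 2 h | 94% | 99.8% | 94% |
| 5 h ECG moved to 8, 12 or 16 h, half-life 6–30 h | 100% | 97–100% | 98–100% |
| Change in points, half-life 6–30 h | +20 to +29 | 0 to +18 | −2 to +17 |

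The late ECG gains coverage only from a half-life of about 10.5 h in Cohort 8 and 14.6 h in Cohorts 9–10. In Cohort 7 it gains throughout the range.

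**The case against.** **Subjects are watched.** Telemetry runs through the infusion, dosing is supervised, and ECGs can be triggered by adverse events or telemetry findings. Triggered tracings also count towards the maximum-QTc summary in Table 14.3.6.2. All of this stands. A reader might infer that subjects go unmonitored for hours; the documents do not support that. Telemetry, however, covers heart rate and rhythm and its results are only listed. It supplies no blood pressure, temperature or scheduled QTc.

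**The 5-minute readings were not cut in minutes.** A reader might infer a cutback, since the February text covers the whole infusion and the SAP only its first 30 minutes. Every February infusion lasted 30 minutes, so the coverage in minutes is the same. It also takes in the fastest part of the infusion, a sensible emphasis when infusion-site and hypersensitivity reactions are the named generic risks. For the same reason the 0.75 h reading should stay.

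**The ECG gap matters less than its 19 hours suggest.** A reader might infer that peak QTc is missed in all four cohorts. In Cohorts 8–10 the loading and middle steps bring the concentration near peak by about 3 to 4 h unless the half-life is long. Protocol 1.3 points to a shorter one: the rat AUC of 23100 and the stated margin of 0.6 imply a predicted human AUC of 23100/0.6 = 38500 µg·h/mL, so clearance is 18000/38500 = 0.47 L/h. A 10.5 h half-life would then need 0.47 × 10.5/0.693 ≈ 7.1 L, and 14.6 h about 9.8 L. The documents state no volume; at an assumed 3–6 L the half-life is 4.4–8.9 h, and a late ECG gains no peak coverage in Cohorts 8–10. Nor is Cohort 7 worse placed than earlier cohorts over the assumed 6–30 h: its 5 h ECG is at 1.07–1.30 times the Cohort 6 concentration at 1 h.

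**Timing and sources.** SAP 3 sets the later regimens from earlier cohorts' data, and the memos for Cohorts 7, 8 and 9–10 are dated 3 July, 25 July and 8 August 2018. Cohort 7, and probably Cohort 8, may already have been dosed. The SAP follows protocol amendment 5, which was not supplied, nor were the memos. Extra readings there are possible. Against that, Table 3-2 refers to the protocol for cohort-specific PK and pharmacodynamic times but writes out the vital-signs and ECG times in full.

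**Conclusion.** The concern holds in a narrow form, as a point to consider. In Cohorts 8–10 no vital signs are scheduled for the last 4.0 h (15% of dose) or 8.3 h (23%) of the infusion. This follows directly from SAP 7.3 and 8.3 and needs no pharmacokinetic assumption. In Cohort 7 the last Day 1 ECG is at about 71–80% of peak, given one compartment and a half-life of 6–30 h; the shortfall shrinks to 6% at 2 h. In Cohorts 8–10 the ECG gap is real, but its cost in peak coverage depends on a half-life that the documents do not give. The defect lies in the data available to the by-time tables, not in the observation of subjects. Confidence is medium, because amendment 5 and the dosing memos could not be checked.

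**What to change.** For cohorts not yet dosed:

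- **Cohorts 8–10:** add one full vital-signs set at the blood draw already scheduled at 12 h (Cohort 8) or 16 h (Cohorts 9–10, 20 minutes before the end). Keep the 0.75 h set.
- **Cohort 7:** move the 5 h ECG to the 8 h draw, where vital signs are already taken. Keep the 1 h and 4 h tracings.
- **Late ECG in Cohorts 8–10:** optional. Decide from the half-life seen in earlier cohorts, using the thresholds of about 10.5 h and 14.6 h.
- **Tables 14.3.5.1 and 14.3.6.1:** label these rows as end of infusion by cohort, with placebo only from cohorts that have the reading rather than the pooled Cohorts 7–10 placebo group.

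Protocol 3.5.5 already sets the order of overlapping procedures: PK blood, ECG, then vital signs. For a cohort already dosed, the report can state that no scheduled reading exists in that interval.

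**Cost.** A short amendment with IRB approval (Protocol 5.2.1) and one extra vital-signs set per subject in Cohorts 8–10. In Cohorts 9–10 that set probably falls at night, against a daytime baseline. Placebo numbers are small: 2 in Cohort 8 and 2 to 4 across Cohorts 9 and 10. Cohort 7 loses the 5 h ECG match to earlier cohorts.

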8.5. Physical Examination and Physical Measurements

Full physical examination (including height, weight, and BMI calculation, assessment of skin, head, ears, eyes, nose, throat, neck, thyroid, lungs, heart, cardiovascular, abdomen, lymph nodes, and musculoskeletal system/extremities) will be performed at screening and Day 28 only. Brief physical examinations will include assessment of skin (including any signs for cutaneous erythema), lungs, cardiovascular system, and abdomen (liver, spleen) and will be performed at Day -3 (Cohorts 4 through 10 only), Day -1 (Cohorts 1 through 3 only), Day 3, and Day 7.

Interim physical examinations will be performed at the discretion of the investigator, if necessary, to evaluate AEs or clinical laboratory abnormalities.

Physical examination data will be listed. Screening height, weight and BMI will be summarized together with demographics variables.

9. Immunogenicity Analysis

Immunogenicity (antibody) samples will be screened for the presence of binding anti-drug antibody (ADA) on Day -3 (Cohorts 4 through 10 only), Day -1 (Cohorts 1 through 3 only), Day 7, and Day 28/EOS. A subject testing positive for ADA at the final planned visit (Day 28) will be asked to return for follow-up sampling approximately 3 months after their final visit and approximately every 6 months thereafter until these no longer test positive or until levels return to a pre-dose state.

The ADA result (positive or negative) will be summarized by treatment group and visit using counts and percentages. All ADA results with corresponding titer values will be presented in a data listing. The neutralizing antibody (NAb) results may be listed and summarized in the clinical study report if the assay is available.

10. Pharmacokinetic Analysis

The PK population will be used for all PK analysis tables and figures.

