4.1. General Data Presentation Rules

All data will be provided in individual by-subject listings.

Data from subjects excluded from an analysis population will be presented in the data listings but not included in the calculation of summary statistics.

Data from subjects receiving placebo will be pooled across cohorts for all presentations.

Unless otherwise noted, the following treatment groups will be used in summaries:

- 100 mg PB2452 (C1)
- 300 mg PB2452 (C2)
- 1000 mg PB2452 (C3)
- Placebo C1-C3
- 1000 mg PB2452 (C4)
- 3000 mg PB2452 (C5)
- 9000 mg PB2452 (C6)
- Placebo C4-C6
- 18000 mg PB2452 (C7)
- 18000 mg PB2452 (C8)
- 18000 mg PB2452 (C9)

- 18000 mg PB2452 (C10)
- Placebo C7-C10
- All Placebo (for safety summaries only)
- All PB2452 (for safety summaries only)
- All subjects

where 'C' means 'Cohort'.

Demographic data, baseline characteristics, adverse events (AEs), laboratory tests, vital signs, 12-lead electrocardiogram (ECG) measurements, and subject disposition will be summarized descriptively.

Unless otherwise noted, the summary of the continuous variables will include the number of subjects with non-missing data (n), mean, standard deviation (SD), median, minimum, and maximum. Categorical variables will be summarized descriptively by their counts and associated percentages. Percentages will be calculated using the number of subjects within a summary group as the denominator.

Minimum and maximum values will be presented as the same precision as the original value. Means and medians will be presented as 1 decimal place greater than the precision of the original value. Standard deviations will be presented as 2 decimal places greater than the precision of the original value. Percentages for summarizing categorical data will be presented with 1 decimal place. If the percentage value is less than 0.1, then "<0.1" will be displayed.

Unless specified otherwise, baseline for safety analyses is defined as the last non-missing measurement (including repeated and unscheduled measurements) prior to the first study drug administration; baseline for PD analyses is defined as the last non-missing measurement (including repeated and unscheduled measurements) prior to the first ticagrelor administration.

Listings will be sorted by treatment group and subject identifier.

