11.1. Pharmacodynamic Data

Blood samples for PD analysis will be collected from subjects in Cohorts 4 through 10 at the following time points: before dosing (within 60 minutes prior to 1st ticagrelor dose on Day -2) and again before dosing (within 10 minutes prior to the initiation of the study drug infusion [Hour 0]), and up to 48 hours after the initiation of study drug infusion. Specific collection times are listed in the table below:

Summary of Pharmacodynamic Assessments	
Cohorts 4-6	Day -2 (60 minutes prior to 1 st ticagrelor dose) and Day 1 (-10 minutes, 0.5, 1, 2, 3, 6, 12, 24 and 48 hours)
Cohorts 7-8	Day -2 (60 minutes prior to first 1 st dose) and Day 1 (-10 minutes, 5 minutes and 0.25, 0.5, 1, 2, 3, 6, 8, 10, 12, 16, 20, 24 and 48 hours)
Cohort 9-10	Day -2 (60 minutes prior to first ticagrelor dose) and Day 1 (-10 minutes, 5 minutes, 0.25, 0.5, 1, 2, 3, 6, 8, 12, 16, 20, 24, 28, 36 and 48 hours)

Platelet aggregation will be assessed using the LTA, VerifyNow, and VASP assays. The results of platelet aggregation from the LTA assay (using 5 μ M ADP and 20 μ M ADP) will be expressed as maximal-extent aggregation (MA), %baseline MA, final-extent aggregation (FA) and %baseline FA, which will be calculated from the platelet aggregation-time profile for each sampling time point. The results for the VerifyNow assay will be expressed as PRU and %baseline PRU, which will be calculated from the platelet aggregation-time profile for each sampling time point. Similarly, PD results from the VASP assay will be expressed as PRI and %baseline PRI, which will be calculated from the platelet aggregation-time profile for each sampling time point. PD data will be listed by subject with ADA status and summarized for each treatment group for each time point using descriptive statistics (number of subjects, mean, SD, median, minimum, and maximum). A ADA-positive subject is defined as a subject with at least one ADA-positive sample at any time during the treatment or follow-up observation period. In case of a positive pre-treatment sample, if the titer of at least one post-treatment ADA is elevated at least 2 folds of the titer in pre-treatment sample, this subject is also ADA positive otherwise ADA negative.

Mean PD data versus scheduled time profiles will be presented graphically.

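### The only planned ADA summary is raw positivity by visit; the SAP's own subject-level definition, with its titer rule for pre-dose positives, is not applied to it

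*SAP*

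**What the plan says.** SAP Section 2.2 makes the immunogenicity potential of PB2452 a secondary objective. SAP Section 9 has ADA samples taken "on Day -3 (Cohorts 4 through 10 only), Day -1 (Cohorts 1 through 3 only), Day 7, and Day 28/EOS", so each subject has one pre-dose and two planned post-dose samples. The planned summary is: "The ADA result (positive or negative) will be summarized by treatment group and visit using counts and percentages". In the list of outputs this is Table 14.3.7, on the Safety population. Titers are listed but not summarized: "All ADA results with corresponding titer values will be presented in a data listing".

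A second rule stands in SAP Section 11.1, in the text on pharmacodynamic data. It works by subject: "A ADA-positive subject is defined as a subject with at least one ADA-positive sample at any time during the treatment or follow-up observation period". For a subject whose pre-treatment sample is positive, it asks "if the titer of at least one post-treatment ADA is elevated at least 2 folds of the titer in pre-treatment sample"; if not, the subject is classed as ADA negative. Its stated use is this: "PD data will be listed by subject with ADA status". PD samples are taken only in Cohorts 4 to 10.

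Two general rules bear on the denominator. SAP Section 4.1 says: "Percentages will be calculated using the number of subjects within a summary group as the denominator". SAP Section 4.7 leaves a subject with missing data out of the statistic concerned. Section 9 does not choose between them.

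**The concern.** The objective asks how many subjects developed or boosted antibodies after PB2452. Table 14.3.7 answers a different question: how many samples were positive at each visit. A subject who was positive before dosing and stays positive adds to the Day 7 and Day 28 counts in the same way as a subject who seroconverted. By-visit counts also do not link visits within a subject.

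The SAP anticipates pre-existing antibodies, since it has a titer rule for them, but applies that rule only in a listing for another endpoint. Two meanings of ADA positive would then stand in one study report. Cohorts 1 to 3, the only cohorts given PB2452 without ticagrelor, would receive a subject-level status in no planned output.

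With 3 or 6 active subjects per group, one subject moves a percentage a long way, so both the classification and the denominator matter to what the table appears to show.

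**Working it through.** The plan states no ADA rate and no power for this objective, so there is no figure of its own to reproduce. The group sizes can be checked.

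**Group sizes (SAP Table 3-1).** Three cohorts of 4 and seven of 8 give 3×4 + 7×8 = 68, which matches the stated maximum in SAP Section 4.2. Actives: 3×3 + 7×6 = 51. If Cohorts 9 and 10 stay at 4 subjects each, actives are 9 + 30 + 6 = 45.

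**1. One subject under the two rules.** Take a Cohort 4 to 10 subject who is positive before dosing, positive at Day 7 and Day 28, and has no 2-fold titer rise.
- Section 9, Table 14.3.7: positive at all three visits.
- Section 11.1, PD listing: ADA negative.

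**2. Size of the mixing.** One such subject adds 1/n to the raw post-dose rate and nothing to the subject-level rate:
- n = 3: 1/3 = 33.3 points
- n = 6: 1/6 = 16.7 points
- n = 51: 1/51 = 2.0 points

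With 6 actives, one such subject and one newly positive subject, all tested, the raw rate is 2/6 = 33.3% and the Section 11.1 rate is 1/6 = 16.7%.

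**3. How likely is at least one pre-existing positive?** The formula is 1 − (1 − p)^n. The prevalence p is an assumption, so a range is shown.

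| Assumed p | n = 6 | n = 51 |
|---|---|---|
| 2% | 11.4% | 64.3% |
| 5% | 26.5% | 92.7% |
| 10% | 46.9% | 99.5% |
| 20% | 73.8% | about 100% |

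**4. What by-visit counts leave open.** In a group of 6 with none positive before dosing, 1/6 at Day 7 and 1/6 at Day 28 may be one subject (1/6 = 16.7%) or two (2/6 = 33.3%). Likewise 1/6 before dosing and 1/6 at Day 28 may mean no new positive, or one new positive with the first subject now negative.

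**5. Denominator.** One positive and one missing sample at a visit:
- n = 6: Section 4.1 gives 1/6 = 16.7%; Section 4.7 gives 1/5 = 20.0%.
- n = 3: 1/3 = 33.3% against 1/2 = 50.0%.

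Under Section 4.1 with n = 6, the negatives are 4/6 = 66.7%. Positive and negative then add to 5/6 = 83.3%, so the missing sample appears as a gap and not as a negative.

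**The case against.** The strongest reply is that nothing is hidden. The pre-dose sample is one of the tabulated visits, so each group's starting positivity stands beside its post-dose counts. The pooled placebo groups show the background rate. Every result and titer is listed, and with 3 or 6 actives per group a reader can work out by hand who changed. The two rules also use different units, sample and subject, and need not agree. No hypothesis test or dose-escalation rule in the documents uses this table. The 17- and 33-point steps are what any single event does in groups of this size. In an All PB2452 column, which Section 4.1 provides for safety summaries, one subject is about 2 points.

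Most of this stands, and it limits the point to a modest one. It does not remove it. The listing lets a reader rebuild the answer, but the SAP would still give no summary of subject-level incidence for a stated objective while holding the definition needed to produce one.

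A reader might also infer from Section 4.1 that missing ADA samples are counted as negative. The documents do not support that. A missing sample has no result to tabulate, Section 4.7 leaves such subjects out, and even over the full group size the negative count would not include them. Nor does Section 9 itself fix the full group size as the denominator. What can be said is that the denominator is ambiguous.

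**Conclusion.** The point holds in a limited form. Table 14.3.7 reports raw positivity by visit. The Section 11.1 subject-level definition is not carried into it and is not planned at all for Cohorts 1 to 3. Pre-existing and induced or boosted antibodies are mixed in the post-dose counts, and one subject can carry opposite labels in two outputs.

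The size is one subject's share of the group at each affected visit: 16.7 points with 6, 33.3 with 3, about 2 with 51. This assumes that at least one subject is positive before dosing, stays positive and has no 2-fold titer rise. The documents give no prevalence from which to judge how likely that is. The denominator question is separate and smaller: 16.7% against 20.0% in the example with 6. The pre-dose visit and the titer listing mean that no information is lost, so this is an improvement to the reporting and not a threat to the study's conclusions.

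**What to change.** 1. Keep the by-visit table. Add to Table 14.3.7 the number and percentage of subjects who are ADA positive under the Section 11.1 definition, by treatment group, for all cohorts including 1 to 3.
2. Use as denominator the subjects with a pre-dose sample and at least one post-dose sample. Section 11.1 does not state this condition, so write it into Section 9 explicitly.
3. State that by-visit percentages use subjects with an ADA result at that visit, and show that number in the table.
4. Place the definition in Section 9 and have Section 11.1 refer to it, so that the report has one meaning of an ADA-positive subject.

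The cost is one added row per group, one denominator rule and a cross-reference. The results and titers are already collected and listed, so no new samples or data are needed.
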